Physicians (n = 70) and staff (n = 40) at CCHMC PPCC will be recruited for this study to evaluate the effectiveness of VICTORI on HPV vaccine initiation and completion rates. Physicians from PPCC will receive \$50 for their efforts. Staff will receive a \$10 gift card for their efforts.

Additionally, physicians (target number = 35) from HSNHC will be recruited to serve as the control. HSNHC participants will receive the self-directed app based curriculum component of VICTORI though will not undergo the VR simulations. Participants from HSNHC will receive \$25 for their efforts.

The primary outcome is the increase in the proportion of patients receiving HPV vaccination seen by resident and attending physicians following participation in VICTORI. These data will be obtained from the EPIC electronic medical record on a monthly timeline from PPCC 6 months prior to implementing VICTORI (baseline), the months during intervention implementation, and 6 months after the intervention (post) for physicians, as well as 6 months after the intervention (post) for staff. These data will be compared with monthly HPV vaccination data from HSNHC from the start of the study until 22 months to serve as a control. Data will be blinded and entered into a REDCap database. The research materials to be obtained from participants are data collected through audio/video recordings during VICTORI and items from validated survey instruments to evaluate secondary outcomes. These secondary outcomes include physicians' behavioral capability, self-efficacy, perceived benefits, barriers, and risk, as well as attitudes, subjective norms, and strength of recommendations. We will also collect data on staffs' behavioral capability, perceived

benefits, barriers, and risk, as well as attitudes, subjective norms and ability to provide consistent positive messaging about the HPV vaccine. We will also collect data on participant characteristics. Survey data will be collected pre-intervention, immediate post-intervention, and 3 months post-intervention for physicians and pre-intervention and immediate post-intervention for staff. Data files will be kept in REDCap. Only study personnel will have access to the data.

Aim 3: Determine modifiable barriers related to HPV vaccine non-completion for future enhancement of VICTORI accordingly.

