anticipate the findings to be generalizable to other urban primary care clinics that serve predominantly minority populations. The PPCC is staffed by approximately 20 attending physicians (total: 8.0 Full-time equivalent), 80 pediatric residents, 25 nurses, 21 medical assistants, 5 nurse care managers, 3 social work care managers, 3 social workers, 1 community engagement specialist, 14 community health workers, 2 customer service representatives, and 6 psychologists. Additionally, we will recruit resident and attending physicians from the HSNHC who will not receive the VR intervention but will serve as controls, only receiving the self-directed app-based curriculum. HSNHC serves a predominantly underserved population as well with 90% publicly insured. Seventy-three percent of the patient population is African American, and 5% is Latino. HSNHC is staffed by approximately 7 attending physicians (total: 2.5 Full-time equivalent) and 28 pediatric residents. HPV initiation rates in Ohio are 57% for girls and 55% for boys; completion rates are 42% for girls and 41% for boys.¹ The completion rate in Hamilton County is 16% for boys and girls combined.⁶⁸ The vaccination initiation rates in the PPCC (FY17) for 11 to 12-year-old girls was 48% (257 vaccinations initiated out of 537 visits) and for 11 to 12-year-old boys was 52% (289 vaccinations initiated out of 557 visits). The HPV vaccination initiation rate in the PPCC (FY17) for 11 to 17-year-old boys and girls was 43% (619 vaccinations initiated out of 1450 visits). The rationale for including adolescents 9 to 17 years old is this will allow us to perform a stratified analysis to determine if the intervention is more effective during the target range (11-12 years), the catch-up range (13-17 years), or early vaccination range (9-10 years). In addition, the National Immunization Survey (NIS) for Teens assesses vaccination rates in children age 13-17 years. By including all children age 9-17 years within our study population, it will allow comparison with the NIS-Teen outcome measures. The PPCC cares for very few patients 18 years and older, and we therefore did not extend our population beyond 17 years. HSNHC, environmental control, had a 51% HPV initiation rate (FY17) for 11 to 17-year-old boys and girls (183 vaccinations out of 357 visits). The HSNHC serves a comparable site to the PPCC and is similarly staffed by physicians from CCHMC though distinct from those physicians practicing at PPCC.

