Next, we will implement VICTORI with staff including nurses and medical assistants in groups of up to 15-20 participants (phase II; secondary outcome). These sessions may take place through a technology-based platform to allow for social distancing dependent on the COVID-19 pandemic and institutional guidelines limiting group meetings and in-person research visits. Staff will watch a 5-minute video on evidence-based practices in recommending the HPV vaccine and observe a facilitator and clinician participating in the VICTORI VR simulations, and then engage in a 5-minute debriefing. Staff will complete a brief pre and immediate post survey assessing their perceived benefits and barriers, subjective norms, and positive messaging about the HPV vaccine on paper or via REDCap. We will collect an additional six months of monthly HPV vaccination initiation and completion data, along with influenza, Tdap, and MCV4. We will collect the same vaccination data from the HSNHC over the same study period to serve as a control. The primary outcome will be the increase in the proportion of patients receiving HPV vaccination seen by resident and attending physicians following participation in VICTORI. Additional secondary outcomes, including physicians' behavioral capability, self-efficacy, perceived benefits, perceived barriers, perceived risk, attitudes, subjective norms, and strength of recommendations, as well as staffs' perceived benefits and barriers, subjective norms, and positive messaging will be assessed via validated survey instruments created by [name] and colleagues (see Appendix B and C).^{41,49,72-76} Physicians' strength of recommendation will be self-reported, which is a common method of measuring this construct.³⁰ In addition, this method (self-reported strength of recommendation) is supported as it is positively associated with vaccination rates documented through medical records.⁷⁷ Physician and staff demographics will also be collected to assess for moderation or confounding. Confidentiality of the results will be maintained. All surveys will have unique IDs with one REDCap form, separate from the surveys including their email and ID. Surveys will also be administered through the REDCap Database. Participants will receive a total of 3 emails encouraging survey completion prior to and following completion of VICTORI. Participants will receive a newsletter periodically via email to enhance retention and provide study updates (appendix). Powerpoint slides will be presented in clinic to as a retention tool as well (appendix).

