physicians (resident and attending combined) enrolled in both the pre- and post-intervention periods. *Secondary analyses* will examine the intervention effect on completion rates, for resident and attending physicians separately, and for all physicians and staff combined. GLMER models as described above will also be used to assess whether background rates of vaccine initiation and completion change over the study period in the absence of the intervention at the control site (HSNHC). Additional secondary analyses will focus on identifying potential mediators of the intervention effect on PPCC providers; whether the effect of the intervention is mediated by changes in the strength of vaccine recommendations and relevant theory-based constructs. Stratified analyses and formal testing of interactions will also be used to assess whether the effect of the intervention differs (i.e. effect modification) according to baseline provider characteristics such as age, sex, and attending vs. resident status, as well as patient characteristics (female vs. male patient, age of patient). As discussed, providers at HSNHC will be receiving the self-directed app-based curriculum component of VICTORI though will not participate in VR simulations and thus will not engage in deliberate practice of curricular skills. HSNHC providers survey responses will be compared to PPCC providers to assess for relevant changes in theory-based constructs including physicians' behavioral capability, self-efficacy, perceived benefits, barriers, and risk, as well as attitudes, subjective norms, and strength of recommendations that might occur following participation in the app-based curriculum only. Survey data will be collected before the app-based curriculum, immediately post-curriculum, and three months after the curriculum. This comparison will be conducted using a two-independent sample t-test.

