Aim 2: Conduct a single-site intervention assessing the efficacy of VICTORI in increasing HPV vaccine initiation and completion rates

Before recruiting any participants, approval from the CCHMC IRB will be obtained. Physicians and staff working in the CCHMC PPCC and attending physicians working in the HSNHC will be sent invitations to participate in the study via email three times over a four-week period. Participants will also be recruited in person. Physicians and staff will be recruited as they were in Aim 1.

Physicians at PPCC and HSNHC will be consented using e-consent. A waiver of documentation of informed consent is requested since no private identifiable health information will be collected and the purpose of the study is to evaluate the effectiveness of VICTORI to increase HPV vaccination rates in clinic. This also aligns with institutional guidelines for remote consenting due to social distancing dependent on the COVID-19 pandemic. A study information sheet will be provided using the REDCap e-consent module. REDCap is a secure web application for building and managing online surveys and databases. While REDCap can be used to collect virtually any type of data (including 21 CFR Part 22, FISMA, and HIPAA-compliant environments), it is specifically geared to support online or offline data capture for research studies and operations. The CCHMC REDCap team has templates available for research use for eConsenting which includes Consent to be a Research Subject and Authorization to Use or Disclose (Release) Health Information that Identifies You for a Research Study (HIPAA). The REDCap electronic consent format does not accommodate the current CCHMC formatting which includes headers with logos and stamps on each page and will therefore require some modifications. Participants will be sent a link to review and complete the e-consent on their own, however, study team contact information will be available for questions. Participants will only be sent the surveys once the participant has electronically agreed to participate in the study, by checking “Yes, I consent to participate in the study”..

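### The PPCC versus HSNHC survey comparison is an unadjusted two-sample t-test with no defined score and no named main follow-up, although baseline, two follow-ups and physician role will be available at both clinics

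*Combined protocol and SAP*

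**What the plan says.** The comparison is in the combined protocol and SAP, Aim 2, Data Analysis: "HSNHC providers survey responses will be compared to PPCC providers to assess for relevant changes in theory-based constructs". The constructs are eight: behavioral capability, self-efficacy, perceived benefits, barriers and risk, attitudes, subjective norms and strength of recommendation. The timing follows ("Survey data will be collected before the app-based curriculum, immediately post-curriculum, and three months after the curriculum"), and then the method: "This comparison will be conducted using a two-independent sample t-test".

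Four other places bear on it:

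- Protection of Subjects, Aim 2, gives the same three waves ("Survey data will be collected pre-intervention, immediate post-intervention, and 3 months post-intervention for physicians") and the group sizes: 70 PPCC physicians, and at the other clinic "physicians (target number = 35) from HSNHC will be recruited to serve as the control".
- Compensation, Aim 2, ties payments at both clinics to the pre, immediate and 3-month surveys.
- Aim 2, Design and Measures, says "Physician and staff demographics will also be collected to assess for moderation or confounding", but names no covariate for this comparison.
- The mixed model earlier in the Data Analysis section is specified for vaccine initiation and completion, not for survey scores.

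**The concern.** A two-sample t-test needs one number per physician. Here that number could be a post score or a change from baseline, at the immediate or the 3-month wave, and the plan does not choose. Two problems follow.

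The first is confounding. The clinic decides the group, and the physicians at the two sites are different people. If post scores are tested, a difference that existed before training is read as a training effect, or hides one.

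The second is selection. If the choice is made after the data are seen, the error rate is no longer the nominal one.

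PPCC physicians complete both the app and the VR session before their first post survey, so change within PPCC cannot separate the two. This between-clinic comparison is where a reader would look for any difference between app plus VR and app alone on the constructs thought to drive the effect.

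**Working it through.** The plan gives no sample size, power, SD, alpha or expected difference for this comparison, so there is no figure to reproduce. What follows is illustration.

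**Inputs from the documents.** 70 PPCC and 35 HSNHC physicians; three waves.

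**Assumed.** Two-sided 5%, SD 1 at each wave, no dropout, no true effect, and equal correlation r between waves of 0.3 to 0.7. The clinic gap g (in SD) is varied.

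**Standard error of a difference in post scores.** s = sqrt(1/70 + 1/35) = sqrt(0.04286) = 0.207.

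**Post scores, persisting gap g.** The t statistic is noncentral with 103 df and noncentrality g/s, and the critical value is 1.983.

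| g (SD) | g/s | False positives |
|---|---|---|
| 0.1 | 0.48 | 7.7% |
| 0.2 | 0.97 | 16.0% |
| 0.3 | 1.45 | 30.0% |
| 0.5 | 2.42 | 66.7% |

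**Change scores, follow-up left open, no gap.** The two change scores share the baseline. Each has variance 2(1 - r) and their covariance is 1 - r, so their correlation is 0.5 whatever r is. For two normal statistics with correlation 0.5, the chance that at least one exceeds 1.96 in absolute value is 9.1%. Simulation with t-tests (40,000 null data sets per r) gives 9.2%, 9.2% and 8.8% at r = 0.3, 0.5 and 0.7.

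**Score and follow-up both left open, no gap.** The chance that at least one of the four t-tests has p < 0.05 is about 16% per construct at each r (same simulations).

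**Which score is safer when there is a gap.** Take g = 0.3 and r = 0.5, with the normal approximation.

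- Stable gap: the change score is unbiased (5%). A baseline-adjusted comparison has bias 0.3 x (1 - 0.5) = 0.15 and standard error 0.207 x sqrt(1 - 0.25) = 0.179, giving 13%.
- Gap shrinking to r x g: the adjusted comparison is unbiased (5%). The change score has bias -0.15 and standard error 0.207 x sqrt(2 x 0.5) = 0.207, giving 11%.

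**Role mix.** Aim 2, Setting and Population, gives about 20 attendings and 80 residents at PPCC (20/100 = 20% attending) and about 7 and 28 at HSNHC (7/35 = 20%).

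**The case against.** **The natural reading is change scores.** This largely stands. The purpose is stated in terms of changes and a pre-survey is described next. Change scores remove a stable clinic gap, so a t-test on them is defensible. A reader might take 30% or 67% as the error rate of the plan. The documents do not support that: those figures need post scores and an assumed gap. On the natural reading, what remains is the unnamed follow-up (9% against 5%, and only if one wave is favoured after the fact) and the absence of any covariate.

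**Change scores might themselves be biased if the gap regresses.** The arithmetic is right, but no physician is selected on baseline score and nothing in the documents gives a reason for the clinic means to converge. It supports a sensitivity analysis, not a charge that change scores are wrong.

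**Role mix might differ by clinic.** A reader might infer this from the recruitment section, where "attending physicians working in the HSNHC will be sent invitations to participate in the study via email", set against Setting and Population: "we will recruit resident and attending physicians from the HSNHC who will not receive the VR intervention but will serve as controls". The inference is weak. Staffing is 20% attending at both clinics, the target of 35 equals the whole HSNHC physician staff (7 + 28) and cannot be met without residents, and recruitment in person is also allowed. Enrolled mixes could differ, since PPCC seeks 70 of about 100, but the documents do not predict it.

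**The purpose is narrower than isolating VR.** The section says the comparison looks at changes after the app alone. No model can separate VR from site with one clinic per arm, so the point should not be argued as a lost causal answer.

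**Confounding and missing data are already handled.** Only in part. Demographics are collected, but no adjusted analysis of this comparison follows. Missing survey data are dealt with under Potential Problems and Alternative Strategies and are not at issue here.

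**Conclusion.** The concern holds in a limited form. The plan tests eight constructs across two non-randomised clinics with an unadjusted t-test, leaves the score undefined and the main follow-up unnamed, and uses neither the repeated measures nor physician role in a model.

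On the likelier reading (change scores), the cost is about 9% false positives per construct instead of 5% if the follow-up is chosen after the data are seen. On the less likely reading (post scores), a persisting gap of 0.2 to 0.3 SD would give 16% to 30%. Both rest on 70 versus 35 physicians with complete data; the second also rests on a gap that the documents do not give, and whose direction is unknown.

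Importance is low to moderate. The outcome is secondary, and neither the primary GLMER nor its power statement depends on it.

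**What to change.** Replace the t-test sentence with one governing analysis:

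> For each construct, a linear mixed model will be fitted to the pre, immediate and 3-month scores with site, wave, site x wave, attending/resident status and status x wave, and unstructured covariance over waves. The site difference in change from baseline at 3 months is the main comparison. The other follow-up will always be reported, as supportive, with 95% CI. A baseline-adjusted model at the main wave is a sensitivity analysis only and does not replace the main result. With one clinic per arm, a difference cannot be attributed to VR separately from site.

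The sponsor may name the immediate wave instead, provided this is done before data are seen. Status x wave is needed because, with complete data, a status main effect cancels out of a change from baseline.

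The plan must say which model governs. If the mixed model and the baseline-adjusted model stood on equal footing, the chance that at least one is significant under no gap and no effect would be about 7% to 8% at one wave and 12% to 14% across both, which brings back much of the flexibility the change is meant to remove.

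The cost is a paragraph of SAP text and slightly more analysis. No new data are needed. The downside is that the sensitivity result may differ from the main one and would then have to be discussed.

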determining whether VICTORI increases vaccine initiation. The PPCC is staffed by 80 residents and 20 attending physicians and reflects the maximum sample size for the intervention. To inform our power calculations for this proposal, we reviewed all PPCC patient visits for 11 to 17-year-old boys and girls from July 1, 2016 to June 30, 2017. HPV vaccination was initiated in 53% of visits for residents and 34% for attending physicians with greater between provider variation for residents. In addition, attending physicians saw more patients (n=9) in this age range on average per month than residents (n=2), and graphical analyses and formal regression modeling did not support material seasonal variation in initiation rates. Simulated outcomes based on these data were used to determine the minimum detectable odds ratio (OR) for vaccine initiation according to study period (i.e. pre- vs. post-intervention) as estimated from the proposed GLMER model. For resident and attending physicians combined, we assumed a total of 70 physicians having on average four patient encounters per month, a baseline probability of vaccine initiation of 43%, and a standard deviation for the subject-specific intercept of 0.55. Study power was determined to be 80% to detect an OR=1.5 based on 10k simulations. *This corresponds to a post-intervention vaccine initiation probability of 53%; or a 10% pre- to post-intervention difference.* Thus, conducting this intervention at CCHMC is expected to provide sufficient power to detect a clinically meaningful effect size for the response.

Potential Problems and Alternative Strategies: Insufficient recruitment may occur, but we do not anticipate this to be an issue as we have successfully conducted a VR intervention focused on flu vaccination with this population.²⁶ In addition, our team and expert consultants have provided extensive recommendations to recruit providers. There is the possibility of incomplete surveys; scale items with <25% missing data will be included in the analysis.⁷⁸ Multiple imputation and/or maximum likelihood estimation will be implemented should material missing values be realized for the survey responses and we will conduct a sensitivity analyses to determine the robustness of study findings to the assumptions of the imputation model.

Aim 3: Determine modifiable barriers related to HPV vaccine non-completion for future enhancement of VICTORI accordingly

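### The power calculation assumes 280 encounters a month, but the protocol's own FY17 count is 121 a month; on that count, power at an odds ratio of 1.5 is about 33–44%, not 80%

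*Combined protocol and SAP*

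**What the plan says.** Aim 2, Power considerations, names the source of its inputs: "we reviewed all PPCC patient visits for 11 to 17-year-old boys and girls from July 1, 2016 to June 30, 2017". From that review it reports that "attending physicians saw more patients (n=9) in this age range on average per month than residents (n=2") and that "HPV vaccination was initiated in 53% of visits for residents and 34% for attending physicians". For the calculation itself, "we assumed a total of 70 physicians having on average four patient encounters per month, a baseline probability of vaccine initiation of 43" per cent, with a standard deviation of 0.55 for the physician intercept. The result is that "Study power was determined to be 80% to detect an OR=1.5 based on 10k simulations", and the section concludes that running the study at this centre "is expected to provide sufficient power to detect a clinically meaningful effect size".

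Aim 2, Setting and Population, gives a count for the same clinic. The FY17 initiation rate at ages 11 to 17 "was 43% (619 vaccinations initiated out of 1450 visits"). For ages 11 to 12 it lists girls ("257 vaccinations initiated out of 537 visits") and boys (289 of 557).

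Aim 2, Data Analysis, specifies a logit mixed model with a physician intercept and fixed terms for study month and period. Period is tested by a likelihood ratio test. Aim 2, Design and Measures, provides six baseline months and six months after physician training.

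**The concern.** The two sections describe one clinic, one age range and, if FY17 means July 2016 to June 2017, one year. Their visit volumes differ by a factor of more than two. The 43% baseline matches the smaller count, while the number of encounters comes from the larger per-physician averages. The simulation therefore combines a rate and a volume that do not fit the same set of visits.

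The claim of adequate power for the primary test depends on which volume is analysable. If it is the smaller one, a true OR of 1.5 would more likely be missed than found, and a null result could be misread as evidence of no effect. The section on Future Use makes these data the basis for a multisite application.

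**Working it through.** **1. Volume.** The assumed average of four follows from the per-physician figures if the 70 are 20 attendings and 50 residents: (20×9 + 50×2)/70 = 280/70 = 4.0. Over 6 + 6 months that is 280×12 = 3,360 encounters. For all 100 physicians (20 attendings, 80 residents): 20×9 + 80×2 = 340 a month, or 4,080 a year. Setting and Population gives 1,450 a year, or 1,450/12 = 120.8 a month. The ratio is 4,080/1,450 = 2.8. Seventy of the physicians cannot have 280 encounters a month in a clinic that has 121.

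**2. Initiations.** The per-physician figures imply 12×(180×0.34 + 160×0.53) = 12×146 = 1,752 initiations a year, against 619 reported. The simulated 3,360 encounters at 43% would give about 1,445.

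**3. Rates.** These agree: (180×0.34 + 160×0.53)/340 = 42.9%, and 619/1,450 = 42.7%. The conflict is in the volume, not the baseline.

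**4. Reproducing the stated 80%.** The protocol does not state alpha, sidedness or the handling of implementation months. I assume two-sided 0.05, six months before and six after, and no gap.

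- A hand check that ignores the physician intercept: each period has 280×6 = 1,680 encounters. The standard error of the log OR without the month term is √[1/(1,680×0.43×0.57) + 1/(1,680×0.531×0.469)] = 0.069.
- Month and period are collinear. Over 12 consecutive months split 6/6 the squared correlation is 0.755, so the variance is multiplied by 1/(1−0.755) ≈ 4.1. The standard error becomes 0.140.
- Power = Φ(ln 1.5/0.1403 − 1.96) = Φ(0.93) = 82%.
- Simulating the full mixed model (intercept SD 0.55, Poisson encounters, maximum likelihood, likelihood ratio test for period, 6,000 replicates) gives 80.2%. The null rejection rate is 4.8% (2,000 replicates).

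**5. The same model at the FY17 volume, OR 1.5.**

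| Encounters per month | Basis | Hand check | Simulation |
|---|---|---|---|
| 280 | 70×4 | 82% | 80.2% |
| 120.8 | all 1,450 visits seen by the 70 | 47.5% | 43.8% |
| 99.5 | 120.8×280/340 (20 attendings, 50 residents: 82% of visits) | 41% | 37.1% |
| 84.6 | 120.8×70/100 (70% of visits, an assumption) | 35.5% | 33.4% |

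The Monte Carlo standard error is about 0.6 points. Repeat simulations gave 77–81%, 43–45%, 37–39% and 30–33% for the four rows.

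**6. Detectable OR.** At 120.8 a month, power is 79% at OR 1.86 and 82% at 1.9. At 84.6 a month it is 76% at OR 2.09 and 82% at 2.15. The OR detectable with 80% power is therefore about 1.9 to 2.1. From 43%, that is a post-intervention rate of about 58–61%, where the protocol states 53%.

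**7. Other readings at 1,450 a year** (the 70 physicians seeing 70% to 100% of visits):

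| Reading | Power at OR 1.5 | Same reading at 280 a month |
|---|---|---|
| One-sided 0.05 | 46–57% | 88% |
| Three implementation months left out | 18–24% | 52% |
| Period switches at each physician's training, 3-month roll-out | 42–54% | 89% |
| The same, 6-month roll-out | 50–65% | 95% |
| 1,094 visits a year added for ages 9–10, at 43% | 52–67% | n/a |

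The 1,094 is the count at ages 11–12 (537 + 557), used only as a stand-in because no volume for ages 9–10 is given. Matching 3,360 would need 3,360 − 1,450 = 1,910 such visits. No reading in this table reaches 80%. One-sided testing combined with the 1,094 extra visits, all seen by the 70, gives 78%.

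**The case against.** **The figures may count different things.** The averages of 9 and 2 might cover only months in which a physician saw such patients, or all patients rather than those able to start the series. The 20 attendings make up only 8.0 full-time equivalents, so not all need be active every month. The 1,450 may itself be filtered: removing ages 11–12 leaves 356 visits at ages 13–17 with 73 initiations (20.5%), so three quarters of the visits fall in two of seven age years. These are possible explanations, but the documents state none of them, and none rescues the calculation. If the averages cover active months only, 70×4 in every month is too many. If they count all patients, 43% is not their initiation rate.

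**The loss depends on the month term.** This is true: without it, power is about 94–96% at 121 a month and 87% at 85. But Data Analysis specifies the month term, and without it power at 280 a month is about 100%, not 80%.

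**Phase II months would help estimate the trend.** With six more months, a common slope and a separate phase II level, power at 121 a month rises to about 55–58%, and to 78% with the 1,094 extra visits. A separate phase II slope, which Data Analysis also allows, would reduce that gain. This design gives 89% at 280 a month, so it does not appear to be the one simulated.

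**The settings are inferred.** Matching 80% makes them plausible, not unique. The 33% figure also assumes that 70% of physicians bring 70% of visits. If the 70 are 20 attendings and 50 residents, the range is 37–44%.

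**It may be too late to change the sample.** The Aim 3 text suggests that much of Aim 2 data collection is past. A corrected figure would still govern how a null result is read.

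**Conclusion.** The concern holds. The mismatch in volume follows directly from the protocol's own figures, given that FY17 is July 2016 to June 2017, and no section resolves it. The stated 80% rests on the larger volume.

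The size of the loss is conditional. It requires that 1,450 a year is the analysable count, and it assumes a two-sided 0.05 test, 6 + 6 months without a gap, and the month-adjusted model. Power at OR 1.5 is then about 44% if the 70 physicians see every visit and about 33% if they see 70% of them. Including ages 9–10 or the phase II months would narrow the shortfall; neither alone closes it in the scenarios tried. The documents do not say which volume is analysable, so the power statement should be corrected or justified before it is relied on.

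**What to change.** - Reconcile 1,450 visits and 619 initiations a year with 9 and 2 patients per physician-month, and define which visits enter the primary analysis.
- Rerun the simulation with volume and baseline rate from that one denominator, for ages 9–17 and for the physicians expected in both periods.
- State alpha, sidedness, the number of months simulated, how implementation months are handled, and whether phase II months enter the model.
- Restate the power at OR 1.5, or give the minimum detectable OR at 80% power.

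The cost is a rerun of an existing simulation and a revised paragraph. No participants are added. The restated power may be less favourable.

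### The stated 80% power assumes four encounters per physician per month, the most that any 70 physicians can average on the plan's own loads; role-proportional enrolment gives 3.4 per month and about 73% power.

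*Combined protocol and SAP*

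**What the plan says.** All references are to the combined protocol and SAP.

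- **Aim 2, Power considerations, the assumption:** "we assumed a total of 70 physicians having on average four patient encounters per month, a baseline probability of vaccine initiation of 43" per cent. The standard deviation of the physician intercept is set at 0.55. Stated power is 80% for an OR of 1.5, equivalent to a rise from 43% to 53%. The plan then concludes that the single site is sufficient.
- **Same paragraph, the source data (ages 11 to 17, July 2016 to June 2017):** "attending physicians saw more patients (n=9) in this age range on average per month than residents (n=2"; and "HPV vaccination was initiated in 53% of visits for residents and 34% for attending physicians".
- **Same paragraph, the pool:** "The PPCC is staffed by 80 residents and 20 attending physicians and reflects the maximum sample size for the intervention".
- **Protection of Subjects, Aim 2:** "Physicians (n = 70) and staff (n = 40) at CCHMC PPCC will be recruited for this study". No split by role is given.
- **Recruitment and Consent Procedure, Aim 2:** clinic physicians are invited by email and in person, with no priority for either role at the intervention site.

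**The concern.** An attending brings 4.5 times as many eligible encounters as a resident (9 against 2). The information in the primary analysis therefore depends on who the 70 physicians are as well as on how many there are. The power paragraph uses one common load of four and does not say which mix of roles produces it.

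If four is reached only with nearly every attending enrolled, the headcount of 70 could be met while the encounters, and the power, fall short. Nothing in the recruitment plan would show this. The 80% figure is the plan's stated ground for calling one site adequate.

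**Working it through.** **Inputs.** Loads of 9 and 2, pool of 20 and 80, 70 physicians, baseline 43%, intercept SD 0.55 and OR 1.5 come from Power considerations. Six months before and six after come from Design and Measures. Fixed terms for month and period with a random physician intercept come from Data Analysis. No significance level is stated there, so two-sided 5% is assumed. No gap between periods and no loss of physicians are also assumed.

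**Step 1: which mix gives four?** With A attendings among 70, the mean is (9A + 2(70 − A))/70.

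- Setting it to 4: 7A + 140 = 280, so A = 20. That is every attending plus 50 residents.
- Because A cannot exceed 20, four is also the maximum.
- Equal uptake (70% of each role): (14×9 + 56×2)/70 = 238/70 = 3.4.
- Whole clinic: (20×9 + 80×2)/100 = 3.4.

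**Step 2: reproduce the plan's 80%.** The linearised model gives SE(log OR) = 1/√(N·w·S).

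- N is encounters per month over all physicians.
- S is the variation in period left after adjusting for month. Over 12 months, S = 12×0.25 − 18²/143 = 0.734.
- w is the mean of p(1 − p) over the two periods and the intercept distribution, which is 0.231.

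At N = 280, SE = 1/√(280×0.231×0.734) = 0.145. Power = Φ(0.4055/0.145 − 1.96) = Φ(0.84) = 79.8%. Simulation with the likelihood ratio test (3,000 runs, four encounters in every month) gives 79.9%, with type I error 5.1%. The stated figure is reproduced. A one-sided 5% test would give 87.5%, so it does not match.

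**Step 3: vary the mix, holding 70 physicians.**

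| Attendings + residents | Encounters/month | Mean | SE | Power at OR 1.5 |
|---|---|---|---|---|
| 20 + 50 | 280 | 4.0 | 0.145 | 79.8% |
| 18 + 52 | 266 | 3.8 | 0.149 | 77.8% |
| 16 + 54 | 252 | 3.6 | 0.153 | 75.6% |
| 14 + 56 | 238 | 3.4 | 0.157 | 73.1% |
| 12 + 58 | 224 | 3.2 | 0.162 | 70.6% |
| 10 + 60 | 210 | 3.0 | 0.168 | 67.8% |

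For 14 + 56, the OR detectable with 80% power is exp((1.96 + 0.8416)×0.157) = 1.55.

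**Step 4: other methods for 14 + 56.**

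- Likelihood ratio simulation at a common load of 3.4: 72.6% to 73.3%.
- Simulation with loads of 9 and 2: 74.0%.
- The same with baselines of 34% and 53%: 71.8%.
- Ignoring the spread of physician intercepts (w = 0.247): 75.9%, detectable OR 1.53. That method gives 82.4% at 20 + 50, so the fall is again 6 to 7 points.

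**Step 5: rounding of 9 and 2.** The proportional mean lies between (14×8.5 + 56×1.5)/70 = 2.9 and (14×9.5 + 56×2.5)/70 = 3.9. Power is then about 66% to 79%.

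**The case against.** The best defence is that nothing stated is miscalculated. The plan presents four as an assumption, the 80% reproduces, and 20 + 50 lies within the pool. The 14 + 56 mix is a reviewer's benchmark; the documents do not forecast equal uptake. All of that stands, so this is an unstated dependence on role mix and not an arithmetic error.

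Three stronger readings are tempting, and the documents do not support them.

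- **That four is possible only with all 20 attendings.** This is exact only if 9 and 2 are exact. With 9.0 and 2.4, a mix of 17 + 53 gives (153 + 127.2)/70 = 4.00.
- **That no set of 70 gives both 43% and four encounters.** With the printed figures, 20 + 50 gives (180×0.34 + 100×0.53)/280 = 40.8%, and 14 + 56 gives (126×0.34 + 112×0.53)/238 = 42.9%. But 17 + 53 at 9.0 and 2.4 gives (153×0.34 + 127.2×0.53)/280.2 = 42.6%, which rounds to 43%. The 43% is also the observed clinic rate (619/1,450 in Setting and Population), so it need not come from any enrolment mix.
- **That the true power is 73%.** Two open questions about the loads prevent this.
  - The loads cover ages 11 to 17, while the trial covers 9 to 17. Going from 3.4 to 4.0 needs 18% more visits. If visits were equal per year of age (an assumption; no count is given), 3.4×9/7 = 4.4.
  - In the other direction, the loads imply 12×(180 + 160) = 4,080 visits a year, against the 1,450 reported for ages 11 to 17. At 1,450/(12×100) = 1.21 per physician per month, power would be about 34%. Averages over active months only might explain the gap, but the text does not say so.

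The effect is also modest: a detectable OR of about 1.55 in place of 1.50.

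**Conclusion.** The point holds as a conditional one. Taking the plan's loads and pool as stated, four encounters per month is a ceiling for 70 physicians, and the recruitment plan does nothing to secure the near-complete attending enrolment behind it. The 80% should therefore be read as a best case. At role-proportional enrolment the plan's own model loses 6 to 7 points, and each attending replaced by a resident costs a little over one point.

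The size rests on a two-sided 5% test, 6 + 6 months with no gap, no physician loss, and loads of 9 and 2 that apply to the analysed population. The last is the weakest assumption. A reader should not conclude that the study is shown to be underpowered, or that 73% should simply replace 80%.

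**What to change.** In Aim 2, Power considerations:

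1. Reconcile the loads of 9 and 2 with the 1,450 annual visits in Setting and Population, and say what visits at ages 9 and 10 are expected to add.
2. Re-run the existing simulation with role-specific loads and role-specific baseline rates (34% and 53%) for the mix that recruitment is expected to produce.
3. Report the power or minimum detectable OR for that mix, with a range over plausible mixes, and state the significance level and sidedness.
4. State that the 80% applies only near full attending enrolment.

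The target of 70 stays as it is. A role quota is not needed: fixing 20 + 50 would require every attending to take part and would cap residents at 50 of 80.

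The cost is one re-run and a few sentences. The downside is a slightly less favourable stated power if the reconciled loads do not support four per month.
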